### **Follow-Up (for in-patients only)**

A member of the Vascular Access Team will see the patient in person three days after peripheral venous cannulation and each day thereafter according to routine practice. At the follow-up evaluation patency of the peripheral venous catheter and any complications associated with the peripheral venous catheter will be clinically assessed and documented. Follow-up will be completed once the patient has been discharged from the hospital or once the peripheral venous catheter placed as part of the study has been removed or replaced.

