### **Secondary Objectives**

- to compare variables representing the ease of peripheral venous catheter placement, complication rates, and durability of the catheter within each study treatment arm

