### **Eligibility Criteria**

The eligibility criteria were chosen to minimize the risk to the study patient by only including patients who are already planned to undergo placement of a peripheral venous catheter and by excluding any high-risk patients. In order to be considered for the study, patients have to meet the following criteria:

a) Inclusion criteria:

- adult in-hospital patients ( $\geq 18$  years of age, inpatient and outpatient setting)
- willing to provide research authorization
- scheduled and consented to undergo peripheral venous cannulation of one of the upper extremities to be performed by one of the members of the Vascular Access Team
- determined to be a difficult peripheral venous access defined by one of the following criteria in alignment to the A-DIVA scale to be assessed by one of the members of the Vascular Access Team [8]:
  - failed inspection for more than one visible or palpable suitable vein through conventional methods
  - failed at least one attempt of peripheral venous cannulation through any methods
  - history of difficult peripheral venous access
  - greatest diameter of target vein less than 3mm determined by conventional methods

b) Exclusion criteria:

- clinical contraindication for placement of peripheral venous catheter, including:
  - severe bilateral upper extremity edema
  - severe bilateral upper extremity skin burn
  - severe bilateral upper extremity cellulitis
  - history of bilateral axillary lymphadenectomy

- known severe cardiovascular or pulmonary compromise demanding minimization of procedure time, such as:
  - severe shock with severe cardiovascular instability
  - active CPR
  - major uncontrolled hemorrhage
  - any condition for which the primary healthcare provider is requesting emergent venous access
- scheduled PICC or midline catheter placement
- non-English-speaking patients if an interpreter is not available
- prisoner and any individual involuntarily confined or detained in a penal institution
- impaired capacity to make informed medical decisions

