### **Data Collection**

*The following variables will be assessed for all study patients at the time of peripheral venous cannulation:*

a) primary outcome measures:

- rate of successful initial placement of a peripheral venous catheter (investigators have up to 30 minutes or ONE attempt before the study allows for change of technique to the preference of the Vascular Access Team member)

b) secondary outcome measures:

- number of required needle sticks before successful placement of a peripheral venous catheter
- type of method that resulted in successful placement of a peripheral venous catheter
- number of visible veins suitable for cannulation (each continuous vein will be counted as one cannulation site)
- IV catheter gauge size utilized after completion of IV cannulation
- target vein location (bend of the elbow, forearm, back of hand, other) and side of extremity (right vs. left)
- use of warming of arm
- procedure time
- procedure associated complications
- Vascular Access Team member experience (years in practice)
- Vascular Access Team member survey:
  - subjective difficulty locating a suitable vein
  - subjective difficulty of venous access
  - subjective reasons for the difficulty of identifying veins
  - subjective impression of locating additional veins with VeinViewer device
  - subjective impression of usefulness of the VeinViewer device in successful placement of a peripheral venous catheter
- Patient survey:
  - usual number of IV attempts required
  - patients' satisfaction after completion of IV cannulation

c) clinical patient demographics will be derived from patient history and/or medical records:

- age
- gender
- height

- weight
- dominant hand
- date of procedure

*The following variables will be assessed for all in-patient study subjects, if available, at the time of follow-up:*

- catheter patency / need for replacement of catheter / type of catheter used for replacement
- presence of complications such as :
  - hematoma
  - phlebitis
  - thrombophlebitis
  - infiltration
  - nerve damage

All abstracted data, including a study number for each patient, will be stored on a password-protected research database on a hospital server at Lahey Hospital & Medical Center. Any identifier, except for date of procedure, will be removed after the follow-up has been completed.

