## **Limitations**

Overall it is felt that the study has a very robust design. Yet, limitations include bias by any Vascular Access Team member who may favor one method and therefore might create more favorable results with the method of subjective preference (observer-expectancy effect and experimenter bias).

The follow-up was felt to be adequate since most complications are expected to present during the hospital stay. However, long-term complications, such as thrombophlebitis, might be slightly underestimated due to its sometimes later presentation even after removal of the catheter or in patients who have been transferred to a different facility with the catheter still in place. Nevertheless, there is currently no reason to believe that long-term outcomes of a successful peripheral venous catheter are dependent on the method of catheter placement and therefore it is not expected that the study results will significantly be affected.

NIR vein imaging might require a learning curve. To minimize the issue, all Vascular Access Team members have been trained with the device and had to use the device independently during routine patient care for at least 20 cases before being able to participate in the study.

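### No complication check is specified between the procedure and day 3, or at removal or discharge, and two sections conflict on whether a patient whose catheter came out early is assessed

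*Combined protocol and SAP*

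**What the plan says.** The Secondary Objectives section sets out "to compare variables representing the ease of peripheral venous catheter placement, complication rates, and durability of the catheter within each study treatment arm". The Data Analysis section says that primary and secondary outcomes will be compared directly between the groups.

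For follow-up, the section headed Follow-Up (for in-patients only) states: "A member of the Vascular Access Team will see the patient in person three days after peripheral venous cannulation and each day thereafter". At these visits "patency of the peripheral venous catheter and any complications associated with the peripheral venous catheter will be clinically assessed and documented". Follow-up ends at discharge or "once the peripheral venous catheter placed as part of the study has been removed or replaced".

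The Data Collection section lists complications at cannulation for all patients. It then lists patency, need for replacement, type of replacement catheter and five named complications under this lead-in: "The following variables will be assessed for all in-patient study subjects, if available, at the time of follow-up". Date of removal and reason for removal are not on the list. Eligibility covers the "inpatient and outpatient setting".

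The Study Monitoring section has a Vascular Access Team member physically evaluate patients on day 3 for procedure-related adverse events. It exempts those who have gone home or are otherwise unavailable in hospital. It does not exempt patients whose catheter is already out.

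The Limitations section says: "The follow-up was felt to be adequate since most complications are expected to present during the hospital stay". The only shortfall it admits is in complications that appear late.

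**The concern.** A catheter that infiltrates or becomes inflamed may be taken out for that reason. If this happens on day 1 or 2, the Follow-Up section regards follow-up as complete before any visit has taken place, and it asks for no record at the point of exit. The loss would then be related to the outcome, because the complication itself can cause the exit.

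What is at stake is the comparison of complication rates and durability between the three arms. If one placement method leads to more early failures than another, that difference arises in the interval with no scheduled look. The Limitations section does not deal with this. It reasons that most complications occur during the stay, but the uncovered interval is the first part of that stay.

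**Working it through.** The plan gives no complication, removal or discharge rate, so there is no figure on this point to reproduce. Its sample size of 125 per group concerns the primary endpoint and does not bear on the matter. The check is a comparison of the two sections, case by case.

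| Patient | Follow-Up section | Study Monitoring section |
|---|---|---|
| In-patient, catheter in place on day 3 | Seen on day 3, then daily | Evaluated on day 3 |
| In-patient, catheter out before day 3, still in hospital | Follow-up already complete | Evaluated on day 3 |
| In-patient discharged before day 3 | Follow-up already complete | Exempt |
| Outpatient | Not covered | Not named; exempt if at home |

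- **Row 2** is a contradiction: the same patient is finished under one section and due for evaluation under the other.
- **Row 3** is a gap under both sections.
- **Row 4** is a gap under the Follow-Up section.
- **In every row**, nothing is specified for the moment of removal, replacement or discharge.
- **Analysis:** the Data Analysis section has no rule for patients without a follow-up assessment.

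**Direction of the possible bias (illustration on assumed rates only).** Take the strict reading of the Follow-Up section, under which nothing before day 3 is captured. Assume constant daily hazards and a 7-day horizon. Let *a* be the hazard of complication-related failure up to day 3, *b* the same hazard afterwards, and *e* the hazard of any other exit.

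- Early incidence = a/(a+e) × [1 − exp(−3(a+e))]
- Still in follow-up on day 3: s = exp(−3(a+e))
- Later incidence among those = b/(b+e) × [1 − exp(−4(b+e))]
- True 7-day incidence = early + s × later

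Let two arms differ only early: a = 0.10 in arm A, a = 0.05 in arm B, and b = 0.05 in both. With e = 0.2:

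- Arm A: early = 0.10/0.30 × [1 − exp(−0.9)] = 0.198; s = 0.407; later = 0.05/0.25 × [1 − exp(−1.0)] = 0.126; true = 0.198 + 0.407 × 0.126 = 0.249.
- Arm B: early = 0.05/0.25 × [1 − exp(−0.75)] = 0.106; s = 0.472; later = 0.126; true = 0.106 + 0.472 × 0.126 = 0.165.

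| e per day (assumed) | True incidence, A vs B | Among catheters in place on day 3, A vs B | Seen after day 3, per patient starting, A vs B |
|---|---|---|---|
| 0.1 | 30.8% vs 21.7% | 15.0% vs 15.0% | 8.3% vs 9.6% |
| 0.2 | 24.9% vs 16.5% | 12.6% vs 12.6% | 5.1% vs 6.0% |
| 0.3 | 20.7% vs 13.1% | 10.8% vs 10.8% | 3.2% vs 3.8% |

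Under these assumptions the early difference disappears among catheters still in place. It reverses slightly if the events seen later are divided by everyone who started. Changing the denominator therefore does not help unless the early events are also collected. This is a worst case: the day-3 evaluation in the Study Monitoring section, or recorded replacements, would recover part of the loss.

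**The case against.** The plan has more safeguards than the Follow-Up section alone suggests.

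- **The day-3 evaluation follows the patient, not the catheter.** A reader might infer that catheters failing early leave the study unassessed. The Study Monitoring section does not support that for anyone still in hospital on day 3. This stands, although the Follow-Up section says the opposite, and a sign that has resolved by day 3 may still be missed.
- **Complications at cannulation are recorded for all patients, and need for replacement is a follow-up variable.** A reader might infer that the complication objective is answered only among surviving catheters. That is too strong. Ending follow-up at removal does not forbid recording the event that ended it; the plan simply does not ask for this.
- **Adverse-event reports are reviewed and data are examined every four weeks.** This stands as a passive route for serious or reported events. It does not supply a rate measured in the same way in each arm.
- **Operators may change technique after one attempt or 30 minutes.** With 50% success assumed in controls, about half of control catheters could be placed by another method. This dilutes any effect of method on early failure, but the comparison by randomised arm remains the relevant one.
- **Percentages of patients lost.** A reader might compute 1 − (1 − h)³ for assumed daily exit rates of 10%, 20% and 30%, obtain 27%, 49% and 66%, and take these as the share unassessed. The rates are not in the documents. The formula also counts every exit, including uneventful discharge, and ignores the day-3 evaluation. It measures neither missed complications nor a difference between arms.

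**Conclusion.** The point holds in a limited form. The plan specifies no ascertainment of catheter complications between the procedure and day 3, and none at removal, replacement or discharge. The Follow-Up and Study Monitoring sections contradict each other for in-patients whose catheter came out before day 3 and must be reconciled. In-patients discharged before day 3 are scheduled for nothing under either section, and outpatients for nothing under the Follow-Up section.

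Early complications that lead to removal can therefore be missed, and this can bias the by-arm comparison of complications and durability. The size is unknown because the documents give no rates; the worked table shows only a possible direction on assumed hazards. The primary endpoint is measured at cannulation, so it and its sample size are unaffected. This should be corrected, but it does not threaten the main result.

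**What to change.** Keep the routine visits as they are and reconcile the Follow-Up and Study Monitoring sections. Then add two things.

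1. **Data Collection.** For each in-patient, complete the existing complication checklist (hematoma, phlebitis, thrombophlebitis, infiltration, nerve damage) from the medical record. Cover the time from placement to removal or discharge, including when this falls before day 3, and add the date of and reason for removal. Do this before identifiers are discarded: the Data Collection and Risks sections remove them, apart from the procedure date, once follow-up is over, after which the chart may no longer be traceable.
2. **Data Analysis.** Report complications by randomised arm among all randomised patients. Give the number in each arm with no post-procedure information, including outpatients. Restricting the denominator to patients who received a study catheter would condition on an event after randomisation.

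The cost is one chart look-up per in-patient, in records the study already uses for demographics, with no extra visit. The drawback is that routine charting may under-record mild events, and the report should say so.

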### Peripheral Venous Cannulation and Randomization of Study Groups

Patients, who meet eligibility criteria and agree to participate in the study after an informed consent process, will undergo simple randomization. A sealed envelope holding the information of the random assignment will be opened by the Vascular Access Team member. Randomization will assign study patients into 1 of 3 groups/treatment arms with a 1:1:1 ratio:

- Placement of a peripheral venous catheter using conventional methods
- Use of VeinViewer to visualize the most suitable target. Once the target has been identified and marked, the device will be placed aside and the peripheral venous catheter will be placed using conventional methods
- Identification of the most suitable target and placement of a peripheral venous catheter under constant imaging with VeinViewer

When the VeinViewer device will be utilized, multiple areas on the patient's upper extremities will be assessed looking for the most suitable access point according to routine clinical practice. There is no restriction in regards to vein diameter, vein length, or relation of veins to joints. The choice of the location for intravenous cannulation, the use of tourniquets, the use of heating devices, and any techniques to palpate the vein will be left to the discretion of the Vascular Access Team member based on routine clinical practice. This study requires an unobstructed view of the subject's arm under standard hospital lighting conditions.

Investigators have up to 30 minutes or ONE attempt before the study allows for change of technique to the preference of the Vascular Access Team member.

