## **Study Monitoring and Safety Plan**

### **Study Monitoring**

After the first patient has been enrolled, the principle investigator will review the collected data every four weeks with other members of the study staff. At each research meeting, the principle investigator will evaluate study progress and assess protocol compliance. This will include the informed consent procedure, compliance with eligibility criteria, and identification of protocol violations. The principle investigator will also review all collected data to verify data accuracy, consistency, and integrity. The patients will be physically evaluated 3 days after the procedure by a Vascular Access Team member according to routine practice, unless discharged home or otherwise not available in-hospital, to assess for procedure related adverse events. The principle investigator will review any reports that could be pertinent to a potential adverse event. The principle investigator will be responsible for reviewing data from any adverse event and determining, if applicable, whether the research should be altered or stopped. Any decision to alter or stop enrollment will be reported to the IRB.

Any untoward medical event considered related or possibly related to study participation will be considered an adverse event. Serious adverse events (SAE) will be defined as stated in the IRB SAE reporting policy. Adverse events will be graded for severity according to NCI-CTCAE (version 4.0). For the purpose of safety reporting, the study period will be considered from the day of the procedure to the day of the last follow-up. All adverse events of grade II or greater attributable to study participation will be reported to the IRB. Multiple occurrences of an adverse event that, based on an aggregate analysis, is determined to be an unanticipated problem independent of the severity grade will be reported to the IRB. Any SAEs related to study participation will be reported within 5 business days of the PI learning of the event.

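### The unmasked operator may also judge catheter complications and patency at in-patient follow-up; another team member could make this routine visit on a form that does not show the arm

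*Combined protocol and SAP*

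**What the plan says.** **Who knows the arm.** Under Peripheral Venous Cannulation and Randomization of Study Groups, "A sealed envelope holding the information of the random assignment will be opened by the Vascular Access Team member". Whoever then places the catheter by the assigned method necessarily knows the arm.

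**Who assesses follow-up.** Under Follow-Up (for in-patients only), "A member of the Vascular Access Team will see the patient in person three days after peripheral venous cannulation". Daily visits follow as part of usual care. At these visits patency is checked, and "any complications associated with the peripheral venous catheter will be clinically assessed and documented". For safety, Study Monitoring says "The patients will be physically evaluated 3 days after the procedure by a Vascular Access Team member according to routine practice". Neither section requires someone other than the operator, and the protocol contains no provision for masking.

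**What is recorded.** Data Collection lists patency, need for replacement, type of replacement catheter, and the presence of hematoma, phlebitis, thrombophlebitis, infiltration and nerve damage. It gives no criteria for deciding whether one of these is present.

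**Why these data are collected.** The secondary objective is "to compare variables representing the ease of peripheral venous catheter placement, complication rates, and durability of the catheter within each study treatment arm".

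**What is said about bias.** Limitations states that "limitations include bias by any Vascular Access Team member who may favor one method" and labels this "observer-expectancy effect and experimenter bias". The one countermeasure in that section, 20 prior uses of the device, is aimed at the learning curve.

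**The concern.** An operator cannot be masked while using or not using the device. The follow-up visit is different: it does not use the device, it is already routine, and nothing in the text ties it to the operator. As written, however, the person who chose the vein, placed the catheter and knows the method may also decide days later whether there is phlebitis or infiltration.

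The outcomes at stake are complication rates and catheter durability, which form part of the secondary objective, and the day-3 adverse-event check. If the arms differ on these outcomes, unmasked assessment is a rival explanation. The data could not address it, because nothing requires a record of who assessed whom. A larger sample does not remove a difference in recording between arms.

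**Working it through.** **1. The text, side by side.**

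| Question | Section | Answer |
|---|---|---|
| Does the operator know the arm? | Peripheral Venous Cannulation and Randomization | Yes |
| Who assesses patency and complications? | Follow-Up | Any team member |
| Who does the day-3 adverse-event check? | Study Monitoring | Any team member |
| Is the operator excluded, or the arm withheld? | None | No |
| Is assessor bias recognised? | Limitations | Yes, without a countermeasure |
| Is there more than one team member? | Institutional Resources | Yes, a leader and members; number not given |

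Self-assessment is therefore permitted, but not prescribed. That another member is available on every shift is an inference, because neither team size nor rota is stated.

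**2. The plan's own figure.** The point depends on no stated number; the sample size only sets the scale. With 50% against 70%, two-sided 0.0167, 80% power and pooled variance under the null:

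n = [z(1−α/2)·√(2p̄(1−p̄)) + z(0.80)·√(p₁(1−p₁)+p₂(1−p₂))]² / (p₂−p₁)²

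= [2.393·√0.48 + 0.842·√0.46]² / 0.04 ≈ 124.2, so 125 per group and 375 in total, as stated. Enrolling 400 gives 400/3 ≈ 133 per arm. Changing the follow-up assessor alters none of these figures.

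**3. What differential recording could do (illustration).** The documents give no complication rate and no detection rate, so every input here is an assumption: the same true rate in both arms (10% or 20%), 90% of complications recorded in control, and 80%, 70% or 60% recorded in a device arm. Follow-up covers in-patients only, so 133 per arm is an upper limit; 80 per arm is an assumed smaller number.

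With recorded rates a and b, d = a−b and m = (a+b)/2, let SE₀ = √(2m(1−m)/n) and SE₁ = √(a(1−a)/n + b(1−b)/n). The chance of a false positive is Φ((d − z·SE₀)/SE₁) + Φ((−d − z·SE₀)/SE₁).

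Example: a = 0.18, b = 0.12, n = 133. SE₀ = 0.0438 and SE₁ = 0.0436, so (0.06 − 1.96·0.0438)/0.0436 ≈ −0.59 and the probability is 27.7%.

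| True rate | Recorded, control vs device | n=133, α=0.05 | n=133, α=0.0167 | n=80, α=0.05 |
|---|---|---|---|---|
| 10% | 9% vs 8% | 6.0% | 2.1% | 5.6% |
| 10% | 9% vs 7% | 9.2% | 3.8% | 7.5% |
| 10% | 9% vs 6% | 15.3% | 7.2% | 11.1% |
| 20% | 18% vs 16% | 7.2% | 2.7% | 6.3% |
| 20% | 18% vs 14% | 14.4% | 6.7% | 10.6% |
| 20% | 18% vs 12% | 27.7% | 15.2% | 18.5% |

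Both levels are shown because the analysis section sets none for secondary outcomes. With equal recording, each test keeps its nominal level.

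**4. Effect on the estimate.** If the true rate is 20% in both arms and 1 in 5 complications is overlooked in one arm, the data show 20% against 20%·4/5 = 16%. With 1 in 3 overlooked, they show 20% against 20%·2/3 ≈ 13.3%.

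**The case against.** The other side has a good deal to say.

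- **This is permission, not contradiction.** No section says that the operator will do the follow-up, and the trial is openly unmasked, with the bias acknowledged. That stands: what is missing is a safeguard, not awareness of the problem.
- **Not everything is impressionistic.** Study Monitoring grades adverse events by NCI-CTCAE version 4.0, and patency and replacement leave less room for judgement. This stands in part. A severity scale does not settle whether phlebitis or infiltration is recorded as present, and the point rests mainly on those findings.
- **A colleague may hold the same preference.** The substitute comes from the same device-trained team, whose members are investigators or collaborators. Changing the person removes ownership of the placement; preference for a method is dealt with only so far as the arm is hidden. This stands, and it is why the form without the arm matters.
- **Masking will be incomplete.** Target sites are marked in the second arm, the patient knows the method, and the chart may show it. This stands.
- **The expectation itself is blurred.** After one attempt or 30 minutes the technique may change, so the catheter seen on day 3 may not have been placed by the assigned method. This stands, and it weakens any link between arm and expectation.
- **The effect may be small.** At 133 per arm, 20% against 16% gives a two-sided p of about 0.40, and 20% against 13.3% about 0.15. This is fair, although a non-significant distortion still biases the estimate.

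A reader might infer that the bias must favour the imaging arms. The documents do not support this: Limitations speaks of any member who may favour one method, so members may differ and their biases may partly cancel. A reader might also infer that masking is straightforward because the catheter looks the same in every arm. Nothing in the protocol says so, and the marking in the second arm counts against it.

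**Conclusion.** The point holds as a cheap improvement of low severity. The protocol allows an operator who knows the arm to judge the complications and patency of a catheter that he or she placed, and it sets no measure against a bias that it names itself.

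The scope is narrow: in-patients only, follow-up outcomes only, and mainly hematoma, phlebitis and infiltration. It would be wrong to read this as a threat to the primary endpoint. Initial placement success is recorded at cannulation, as are most secondary measures, and the follow-up assessor has no bearing on them.

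Direction and size are unknown. Under the stated assumptions, a nominal 5% test ranges from 5.6% (80 per arm, mild difference in recording) to 27.7% (133 per arm, 20% true rate, large difference), so from slight to substantial. These figures show what is possible and do not estimate what will happen. The remedy also assumes that a second team member is usually available, which is likely in a team of several but is not stated.

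**What to change.** Add the same wording to Follow-Up and to the day-3 check in Study Monitoring, for example:

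> Where the rota allows, follow-up is done by a Vascular Access Team member who did not place that catheter, on a form that does not show the allocation. The assessor's code is recorded, and whether the assessor knew the arm.

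Then:

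- Flag visits done by the operator or with the arm known, and report their number by arm.
- Repeat the comparison of follow-up outcomes without the flagged visits, as a sensitivity analysis. Site marking may make flags more common in the second arm, so the result should be read as supportive only.
- State residual unmasking through skin marks, the chart or the patient in Limitations.

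The cost is a short addition to two sections, a form without the arm, and a code field. There is no extra visit or procedure, and no change to sample size, power or alpha. The downsides are a constraint on the rota and masking that will be only partial.
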